3.8 Premature Withdrawal from Study

Subjects may withdraw at any time, or be dropped from the study at the discretion of the investigator should any untoward effects occur and/or for safety reasons. In addition, a subject may be withdrawn by the investigator or Sponsor if he/she violates the study plan

or for administrative reasons. The investigator or study coordinator must notify the Sponsor immediately when a subject has been withdrawn due to an adverse event.

The circumstances above are referred to as premature withdrawal from the study, and the reason for premature withdrawal should be clearly documented and detailed in the source documentation. The investigator should make every attempt to evaluate the subject's safety, including resolution of ongoing AEs, at the time of premature withdrawal. If a subject wants to withdraw from the study prior to the last planned study visit, the subject will be asked to be followed for safety for the duration of the study. When a subject withdraws, or is withdrawn, from the study, the procedures described in [section 5.5.1, Early Termination Visit](#) should be completed if possible.

The reasons for premature withdrawal from the study include: Adverse event, death, withdrawal of consent, lost to follow-up, administrative reason, and protocol deviation. These reasons are described in greater detail below.

Adverse Event

For any subject withdrawn from study participation prior to the planned Study Termination Visit, it is important to determine if an AE was associated with the reason for discontinuing the study. This AE must be identified on the AE CRF page by indicating "Withdrawn from study due to AE". Any ongoing AEs at the time of study withdrawal must be followed until resolution or stabilization.

Death

For any subject withdrawn from study participation due to death, this should be noted on the Study Termination CRF page and the associated SAE that led to the death must be reported.

Withdrawal of consent

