		Grade 1 Mild	Grade 2 Moderate	Grade 3 Severe
Injection site Erythema (Captured as measurements in millimeters)	1-24 mm	25-50 mm	51-100 mm	> 100 mm

Injection site Induration (Captured as measurements in millimeters)	1-24 mm	25-50 mm	51-100 mm	> 100 mm
Injection site Pain	No pain	Present but does not interfere with activity	Interferes with activity	Prevents daily activity

Solicited Systemic Adverse Events

These include headache, arthralgia, chills, fatigue, malaise, myalgia, and fever (body temperature measured orally). They will be assessed using the scoring system reported in a table below.

Table 7 Grading of solicited systemic adverse events

Solicited systemic adverse events	Grade 0 Absent	Present - Grading of Severity*		
		Grade 1 Mild	Grade 2 Moderate	Grade 3 Severe
Headache	No headache	Present but does not interfere with activity	Interferes with activity	Prevents daily activity
Arthralgia	No arthralgia	Present but does not interfere with activity	Interferes with activity	Prevents daily activity
Chills	No chills	Present but does not interfere with activity	Interferes with activity	Prevents daily activity
Fatigue	No fatigue	No interference with activity	Some interference	Significant; prevents daily
			with activity	activity
Malaise	No malaise	No interference with activity	Some interference with activity	Significant; prevents daily activity
Myalgia	No myalgia	Present but does not interfere with activity	Interferes with activity	Prevents daily activity
Fever as a Body temperature (Captured as measurements in degrees Celsius)	≤ 37.9 °C	≥ 38.0 – 38.9°C	≥ 39.0 – 39.9°C	≥ 40.0°C
	Oral Temperature: <35.5 °C to ≥38.0 °C			

Other Solicited Adverse Events

These include use of analgesics/antipyretics. It will be assessed using the scoring system reported in a table below.

Other Solicited adverse events	Grade 0 Absent	Present - Grading of Severity			
		Grade 1 Mild	Grade 2 Moderate	Grade 3 Severe	
Use of analgesics/ antipyretics		Categorized as “yes” or “no”			

The study staff must review the data entered into the Subject Diary as described in [section 3.4.2, Tools Used for Data Collection](#) and [section 5.3.1, Follow-up Clinic Visit\(s\)](#).

Note: Any solicited adverse event that meets any of the following criteria must be entered into subjects’ source document (see [section 9.1, Source Documentation](#)) and also as an adverse event on the Adverse Event CRF:

- Solicited local or systemic adverse event that continues beyond day 7 after vaccination.

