- Solicited local or systemic adverse event that leads to a visit to a healthcare provider (medically attended adverse event, see [section 7.1.3, Evaluation of Adverse Events](#)).
- Solicited local or systemic adverse event leading to the subject withdrawing from the study or the subject being withdrawn from the study by the investigator (adverse event leading to withdrawal, see [section 7.1.3, Evaluation of Adverse Events](#)).
- Solicited local or systemic adverse event that otherwise meets the definition of a serious adverse event (see [section 7.1.4, Serious Adverse Events](#)).

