8.4.2.1.3 Analysis of Unsolicited Adverse Events

This analysis applies to all adverse events occurring during the study, judged either as probably related, possibly related, or not related to vaccination by the investigator, recorded in AE CRF, with a start date on or after the date of vaccination. AE starting prior to the vaccination will only be listed. The original verbatim terms used by investigators to identify adverse events in the CRFs will be mapped to preferred terms using the MedDRA dictionary. The adverse events will then be grouped by MedDRA preferred terms into frequency tables according to system organ class.

All reported adverse events, as well as adverse events judged by the investigator as at least possibly related to study vaccine, will be summarized according to system organ class and preferred term within system organ class. These summaries will be presented by vaccination group and by interval of study observation. When an adverse event occurs more than once for a subject, the maximal severity and strongest relationship to the vaccine group will be counted.

Separate summaries will be produced for the following categories:

- Serious adverse events
- Adverse events that are possibly or probably related to vaccine

- Adverse events of special interest
- New onset of chronic disease
- Potential immune-mediated diseases (pIMDs) adverse event leading to withdrawal • Adverse events leading to a medically attended visit
- Adverse event by data source.

Data listings of all adverse events will be provided by subject. In addition, adverse events in the categories above will be provided as listed data.

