Clinically significant modifications in hematology will be assessed by medical judgment and recommendations from CBER FDA guidance for Industry; Toxicity Grading

Vaccination Procedure:

All eligible subjects will receive one intramuscular vaccination with GVGH *S. sonnei* 1790GAHB vaccine. Subjects will be observed at the clinic site for 4 hours after vaccination. Safety procedures:

All subjects providing informed consent will undergo review of medical history, a general physical examination including vital signs measurement (temperature, respiratory rate, heart rate, blood systolic and diastolic pressure) at the screening visit (study Days 21 to-1)

and at Visit 1 (Day 1). At clinic Visit 2 and at subsequent visits, a brief symptom-directed physical examination (if necessary according to symptoms the subject has reported) will be performed.

For all women of childbearing potential before vaccination at visit 1, a urine pregnancy test will be conducted and will also be repeated at visit 5 (Day 85).

Procedure for Collection of Solicited AEs:

Beginning in the evening following study vaccine administration (approximately 6 hours), and daily during the 6 days following vaccination, diary cards will be used to collect solicited local and systemic adverse events including other reactions (i.e. body temperature measurements and use of analgesics/antipyretics).

A reminder phone call will be performed or an email will be sent by the site staff to the subject 2 and 6 days following vaccination to remind subjects that the diary card should be completed. Seven days following vaccination, a clinical visit (Visit 2) will be performed at the study site and all information recorded in the diary card will be reported on e-CRF.

In addition to the solicited adverse events data, any unsolicited AE, solicited local and systemic AE that continue at 7 days after study vaccination (Visit 2), will be collected and recorded at V2, V3 and V4 by clinical study staff.

All Serious Adverse Events (SAEs), all AEs leading to vaccine/study withdrawal, all Adverse Events of Special Interest (AESI, see below) and all concomitant medications associated with those events, will be collected from the time of vaccination (visit 1) to study termination (visit 5).

Reactive arthritis and neutropenia will be collected and analyzed as AESIs for this study.

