6.5.2.3. Unsolicited Adverse Events

All the unsolicited adverse events occurring during the study, judged either as probably related, possibly related, or not related to vaccination by the investigator, will be recorded. The original verbatim terms used by investigators to identify adverse events in the CRFs will be mapped to preferred terms using the MedDRA dictionary. The unsolicited adverse events will then be grouped by MedDRA preferred terms into frequency tables according to system organ class. Adverse events judged by the investigator as at least possibly related to study vaccine will be summarized by vaccine group, according to system organ class and preferred term within system organ class. When an unsolicited adverse event occurs more than once for a subject, the maximal severity and strongest relationship to the vaccine group will be counted.

Only vaccine-emergent adverse events (see **section 7.1** of protocol for definition) will be analyzed, i.e., excluding those after a subject has given informed consent but before vaccination.

The summaries will be presented for all study period and will include frequency distributions of the different adverse events:

- Onset between day 1 and study termination (all study period).

The analysis of unsolicited adverse events comprises the following categories:

- Any unsolicited adverse event.
- Possibly or probably related unsolicited adverse events.
- Unsolicited adverse events leading to death.
- Serious adverse events.
- Possibly or probably related serious adverse event.
- Unsolicited adverse events leading to premature withdrawal from study.
- Unsolicited adverse events leading to hospitalization.
- Unsolicited adverse events of special interest.

- Solicited adverse events continuing beyond day 7 will be coded by MedDRA and combined with the respective unsolicited adverse events.

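### As worded, SAP 6.5.2.3 can leave a short-lived solicited reaction that causes a withdrawal out of the withdrawal table

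*SAP*

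**What the plan says.** **SAP.** Section 6.5.2.3 lists the categories of its unsolicited-event analysis. The one on withdrawal is "Unsolicited adverse events leading to premature withdrawal from study". The last bullet of the list is the only rule that brings solicited events in: "Solicited adverse events continuing beyond day 7 will be coded by MedDRA and combined with the respective unsolicited adverse events". Section 2, on collection, is not restricted in this way: what is collected from vaccination to study end is "all AEs leading to vaccine/study withdrawal". Section 6.5.2.4 adds a combined summary of solicited events of any duration and unsolicited events, but names no withdrawal category for it. Section 9 (changes from planned analyses) reads as not applicable.

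**Protocol Version 2.** Section 7.1.1 gives four conditions under which a solicited event goes into the source document and "also as an adverse event on the Adverse Event CRF": it lasts past Day 7, it is medically attended, it leads to withdrawal, or it is serious. The third reads "Solicited local or systemic adverse event leading to the subject withdrawing from the study or the subject being withdrawn from the study by the investigator". Section 3.8 says of the event behind a withdrawal, "This AE must be identified on the AE CRF page by indicating" that the subject was withdrawn because of an AE. It draws no line between solicited and unsolicited events. Section 8.4.2.1.3 opens "This analysis applies to all adverse events occurring during the study, judged either as probably related, possibly related, or not related to vaccination by the" (sentence cut here). It fixes the scope as events recorded in the AE CRF that start on or after the vaccination date. Its separate summaries include events leading to withdrawal, without the word unsolicited.

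**The concern.** The SAP category is narrower than the protocol analysis it implements, and the narrowing is not declared. The trial gives one injection and follows reactions by diary for a week, so a solicited reaction in that week is a natural candidate for an AE that makes someone leave. That kind of event is what the SAP wording can omit. The withdrawal table could then read zero while an AE CRF record carries the withdrawal flag. A reader of the study report would not learn from that table that a vaccine reaction had ended someone's participation.

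**Working it through.** No formula applies and the plan states no figure on this point. The check follows one event through both documents.

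**Test case.** A diary-recorded fever or myalgia starts on Day 2, is not serious, makes the subject leave, and resolves on Day 4.

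| Step | Source | Result |
|---|---|---|
| Is it entered on the AE CRF? | Protocol 7.1.1, withdrawal condition | Yes, whatever its duration |
| Is it flagged as the reason for leaving? | Protocol 3.8 | Yes |
| Is it in the protocol's AE analysis? | Protocol 8.4.2.1.3, scope set by AE CRF entry | Yes |
| Is it in the protocol's withdrawal summary? | Protocol 8.4.2.1.3 | Yes |
| Is it an unsolicited event by definition? | Protocol 7.1.2 (one not solicited through the Subject Diary) | No, read literally |
| Does the SAP merge rule bring it in? | SAP 6.5.2.3, last bullet (past Day 7 only) | No |
| Is it in the SAP withdrawal category? | SAP 6.5.2.3 | No, read literally |
| Is it shown elsewhere? | SAP 6.5.2.2 and 6.5.2.4 | Yes, but not as a withdrawal |

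**Does the word unsolicited restrict the SAP category?** Two features of SAP 6.5.2.3 suggest that it does.

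1. In the same list, the two serious-event categories carry no such qualifier, while those for death, withdrawal, hospitalization and special interest do.
2. If every AE CRF record were already included, the Day 7 rule would not be needed for inclusion, because protocol 7.1.1 already sends those events to the AE CRF. Stating one of four conditions suggests that the merge is limited to that one.

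**A side effect.** Under protocol 3.4.2, a solicited symptom first reported verbally must be described as unsolicited and entered on the AE CRF. Under the literal SAP wording, whether the same reaction counts as leading to withdrawal could therefore depend on whether it was spoken or written in the diary.

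**Size, for illustration.** Planned numbers are from SAP Table 2-1.

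- Previously vaccinated: 5 + 4 + 2 + 4 + 5 = 20. One omitted case gives 0/20 instead of 1/20 = 5.0%.
- Placebo plus naïve: 4 + 26 = 30. One omitted case gives 0/30 instead of 1/30 = 3.3%.
- All subjects: 20 + 30 = 50. One omitted case gives 0/50 instead of 1/50 = 2.0%.

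**The case against.** The strongest defence is that unsolicited is shorthand for recorded on the AE CRF. Protocol 8.4.2.1.3 has the same heading as the SAP section, yet its scope is AE CRF entries. Protocol 3.4.2 applies the word to solicited symptoms reported verbally. SAP section 9 claims no departure. If the table is built from flagged AE CRF records, the test case is counted. This stands to the extent that a reader might infer the event is certain to be missing, and the documents do not support that. They do not show how records will be selected: the SAP refers to a list of tables and to standard mock tables that are not reproduced in it.

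Section 9 is weak support for that defence, however. The SAP list also omits the protocol's summaries of medically attended events, new chronic disease and potential immune-mediated disease, again with no change declared.

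Three further limits stand.

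- A reader might extend the point to hospitalization. Protocol 7.1.4 makes hospitalization a criterion of seriousness, so such a reaction would normally be shown in the SAP's serious-event categories, which carry no unsolicited qualifier.
- A reader might infer that every solicited event resolving by Day 7 is affected. Only those that cause withdrawal can drop out of this category. The rest are tabulated by severity as planned.
- Withdrawal is not a listed safety endpoint, and the safety objective evaluates both groups without a formal comparison. The test case still counts under the solicited-reaction endpoint, and protocol 8.4.2.1.3 calls for by-subject listings of all AEs.

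**Conclusion.** The mismatch is real and its severity is low. The SAP states a rule that, taken at its word, gives a withdrawal count different from the one the protocol plans. This is a wrong selection rule for one table and does not involve lost data: the event is collected, flagged and shown elsewhere in either case.

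The conclusion rests on reading the SAP category literally with the definition in protocol 7.1.2. It also needs at least one withdrawal caused by a non-serious solicited reaction that resolves by Day 7. The documents give no rate for that. In a single-dose descriptive trial of up to 50 subjects it may never occur. The 5.0% and 3.3% figures show what one hypothetical case would do on planned group sizes and are not an estimate of impact.

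**What to change.** In SAP 6.5.2.3:

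1. Rename the category as adverse events (solicited or unsolicited) leading to premature withdrawal from the study.
2. State that it includes every AE CRF record flagged as leading to withdrawal, regardless of duration.
3. Extend the last bullet from events lasting past Day 7 to all solicited events entered on the AE CRF under protocol 7.1.1: past Day 7, medically attended, leading to withdrawal, or serious.

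If the narrower category is intended, declare it in SAP section 9 with a reason. The hospitalization category needs no change on this ground.

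The cost is a few lines of SAP text and a check of the record selection for one table. The data and the flag are already on the AE CRF, so no new collection is needed.

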6.5.2.4. Combined Solicited and Unsolicited Adverse Events

A summary of subjects with all combined solicited (regardless of their duration) and unsolicited adverse events will be provided. Solicited adverse events will be coded by recent MedDRA.

Solicited symptoms are:

Local: Injection site Erythema, Injection site Induration, Injection site Pain

Systemic: Headache, Arthralgia, Chills, Fatigue, Malaise, Myalgia, Fever as a Body temperature

For clintrial.gov and EudraCT posting purposes, a summary of combined solicited and unsolicited non-serious adverse events will be produced by System Organ Class and preferred terms and according to occurrence of each event.

6.5.2.5. Clinical Safety Laboratory Investigations

The investigator must assess all safety laboratory results (see **section 7.1.7** of the study protocol). Clinically significant modifications in hematology test values will be assessed by medical judgment based on interpretation of deviations from the institution's normal values.

All laboratory safety data will be analyzed descriptively by study group. Safety laboratory data will be shown in a 3 x 3 table by visit using categorization of laboratory according to institutional normal reference range (below, within, above).

The frequencies of subjects with clinical laboratory values below, within, or above normal ranges and change-from-baseline values will be tabulated for each clinical laboratory variable by vaccine-group and time-point of assessment (3 x 3 shift tables).

Laboratory values that are outside the normal range will also be flagged in the data listings, along with corresponding normal ranges and assessment of clinical significance.

For subjects presenting at least one clinically significant value, an additional listing will be provided of all laboratory results by vaccine group, by subject, and by relevant parameter. Clinical significance assessed by the investigator will be presented.

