A blood sample will be obtained as part of the initial screening for hematology and serology (HIV, hepatitis B and C, and for HLA-B27 testing only for naïve subjects). Blood will be collected for hematology also on day 8 and 85 (visit 2 and 5 respectively). Each consented subject will have blood collected before vaccination on day 1 for baseline immunological testing and on day 8, 15, 29 and 85 (visit 2, 3, 4, and 5 respectively) post vaccination for immunological. Additional blood draw for preparation of standard serum will be done on day 29 post vaccination (visit 4). Urine pregnancy test will be done at visit 1 prior to vaccination and at visit 5. All individuals with neutropenia occurring at any time during the study will have additional blood draws to repeat complete blood count on a weekly basis until the neutropenia resolves. If neutropenia occurs at the last study visit, Complete Blood Count to be repeated on a regular basis until resolution (for classification of neutropenia during the trial, refer to [Section 5.4 Unscheduled Visits](#)).

Subjects will be observed at the clinic for 4 hour after vaccination on visit 1. Vital signs will be collected before vaccination and at 30 minutes and 4 hours post vaccination. Before leaving the clinic, they will be given a paper dairy card and trained to record in any adverse events occurring before visit 2 and will be reminded by phone call or email on day 3 and 7 post vaccination. These dairy cards will be collected and reviewed on day 8 post vaccination (visit 2).

Any unsolicited AE until visit 4, SAEs until study termination, all AEs leading to study withdrawal, reactive arthritis and severe neutropenia (AESI) and all concomitant medications associated with those events, will be collected and recorded in the subject's source document and in the eCRF. Further details on study procedure are found in [sections 5, Study Procedures and 7, Assessments](#).

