Body temperature measurement is to be performed using the thermometer provided by the site. If the subject feels unusually hot or cold during the day, the subject should check body temperature. If the subject has fever, the highest body temperature observed that day should be recorded on the Diary Card. The collection of body temperature, solicited local adverse events, solicited systemic adverse events will continue for a total of 7 days on the Diary Card. Unsolicited adverse events and medications will be collected by the site staff on the source document at the next planned visit based on subject's interview or when reported by the subject to the site staff by phone/unplanned visits.

At the end of the observation period, the site should schedule the next study visit with the subject. The subject will receive a study ID card to be used as a written reminder of the next planned study activity and to provide study staff contact details. The subject will be reminded to complete the Diary card daily and to contact the site if there are any questions and to contact the site immediately (or as soon as the subject is medically stable) if the subject has a medical condition that leads to a hospitalization or an emergency room visit.

The site staff/doctor should instruct the subject to contact the study doctor immediately in case of fever. All subjects presenting with a history of fever or any other sign or symptom judged by the investigator to be as a result of an infection within 21 days of vaccination will have a blood sample collected for a complete blood count to establish the absolute neutrophil count. If there is a neutropenia, the subject will be managed appropriately according to local and international requirements.

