5.3.2 Safety Follow-up Calls

No safety follow up call will be made in this study. [5.4](#)

Unscheduled Visits

An unscheduled visit describes a non-routine study visit triggered by a specific event. These could include anticipated or unanticipated adverse events or interventions. Data obtained from such unscheduled visit should be record in a respective source document and eCRF.

If a case of neutropenia is observed after vaccination and still prevalent on a subsequent visit, the results will be recorded in the Unscheduled Lab eCRF.

All individuals with a neutropenia, occurring at any time during the study, will have additional blood draws for complete blood count to be repeated on a weekly basis until the neutropenia resolves. If neutropenia occurs at the subject's last study visit, the complete blood count will be repeated on a regular basis until resolution. For classification of neutropenia during the trial, refer to [section 7.1.4.1 Adverse Events of Special Interest](#).

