4. ENDPOINTS

Primary Efficacy/Safety Endpoint(s):

This study has no primary efficacy or safety endpoints.

Primary Immunogenicity Endpoint(s)

Memory response, against the OAg of *S. sonnei* will be evaluated by measuring IgG Geometric mean concentrations (GMCs) 7 days after vaccination as determined by ELISA with O-antigen containing LPS as coating antigen.

Secondary safety endpoint(s):

The measures of safety will include:

- a. Numbers of subjects with deviations from normal values of hematological tests after vaccination.
- b. Numbers of subjects with solicited local and systemic reactions during 7 days following vaccination. Solicited local reactions include injection site erythema, injection site induration and injection site pain; solicited systemic reactions include headache, arthralgia, chills, fatigue, malaise, myalgia, and fever (as measured orally).
- c. Numbers of subjects with reported unsolicited adverse events (of any nature and severity) during 84 days following vaccination.

d. Number of subjects with reported SAEs throughout the study duration.

Secondary Immunogenicity Endpoint(s)

- a. IgG Geometric mean concentrations (GMCs) at 7, 14, 28 and 84 days after vaccination as determined by ELISA and applicable geometric mean ratios between post vaccination and baseline samples.
- b. Number and percentage of subjects with seroresponse for anti- LPS *S. sonnei* at 7, 14, 28 and 84 days after vaccination. Seroresponse is aimed to define a significant increase in post vaccination samples based on the biological performance of this specific serology assay and it is defined as follows:
 - If the baseline value is greater than 50 ELISA Units (EU) then an increase of at least 50% in the post-vaccination sample as compared to baseline [i.e. $((\text{Post-vac} - \text{baseline})/\text{baseline})100\% \geq 50\%$].
 - If the baseline value is less or equal to 50 EU then an increase of at least 25 EU in the post-vaccination sample as compared to baseline [i.e. $(\text{Post-vac} - \text{baseline}) \geq 25 \text{ EU}$].
- c. Number and percentage of subjects with titers post vaccination concentration ≥ 121 EU/ml for anti-LPS *S. sonnei* at 7, 14, 28 and 84 days after vaccination.

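### SAP 6.5.2.5 plans no summary that counts each subject once for secondary safety endpoint (a), and gives no rule for unscheduled haematology

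*SAP*

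**What the plan says.** SAP section 4 defines endpoint (a) as "Numbers of subjects with deviations from normal values of hematological tests after vaccination". Protocol 8.1.2.1 uses the same words. Neither says whether subjects are counted per variable or across variables, how the post-vaccination visits are combined, or whether unscheduled samples count.

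SAP 6.5.2.5 sets the laboratory summary: "Safety laboratory data will be shown in a 3 x 3 table by visit using categorization of laboratory according to institutional normal reference range". It adds that the frequencies of subjects below, within or above range "will be tabulated for each clinical laboratory variable by vaccine-group and time-point of assessment (3 x 3 shift tables"). Protocol 8.4.2.1.4 prescribes the same by-visit 3 x 3 table, so the SAP follows the protocol here.

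The same SAP section plans two listings. "Laboratory values that are outside the normal range will also be flagged in the data listings", with the normal ranges and the assessment of clinical significance. Also, "For subjects presenting at least one clinically significant value, an additional listing will be provided of all laboratory results by vaccine group, by subject".

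On sampling, Protocol 3.1 gives two scheduled post-vaccination draws: "Blood will be collected for hematology also on day 8 and 85 (visit 2 and 5 respectively"). There are two further sources. Under Protocol 5.2.1, subjects with a history of fever or signs of infection "within 21 days of vaccination will have a blood sample collected for a complete blood count to establish the absolute neutrophil count". Under Protocol 5.4, neutropenia leads to weekly repeat counts until it resolves; where it persists at a later visit, "the results will be recorded in the Unscheduled Lab eCRF". Data from unscheduled visits generally also go to the eCRF.

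**The concern.** The endpoint is stated as subjects over the whole post-vaccination period. The planned tables give, for each variable, group and visit, how many subjects were out of range at that visit. A subject abnormal at both visits is counted in two tables, and nothing in the tables shows that it is one person.

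The unscheduled counts raise a second question. A value first found out of range on, say, Day 13, in a subject who was normal at Visit 2 and is normal again at Visit 5, has no stated cell in a by-visit table.

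SAP section 7 makes every analysis descriptive, so the tabulated counts are the safety result. Elsewhere the SAP does combine over time: for solicited events, 6.5.2.2 takes maximum severity over the interval and the occurrence of at least one event. The laboratory endpoint has no equivalent.

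**Working it through.** No sample-size, power or error-rate figure bears on this point. The check is whether each planned output yields the endpoint.

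**Inputs**
- Variables measured after vaccination: 10. Protocol Table 3 lists 11 haematology tests, and prothrombin time is done at screening only.
- Scheduled post-vaccination visits: 2 (Days 8 and 85).
- Planned subjects: 5 + 4 + 2 + 4 + 5 = 20 boosted, 4 former placebo recipients, 26 naïve. 20 + 4 + 26 = 50, which matches the planned total.
- Visit 2 window: 7 days after vaccination, 0 to +1 day (Protocol Table 2, version 2), which is Days 8 to 9.
- Abnormality and fever rates: not given in the documents.

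**Can shift-table counts be added?** If the tables show m1, m2, ... subjects out of range among N, the number with at least one abnormality lies between max(m) and min(N, sum of m).

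*One variable, two visits.* Assume 3 at Visit 2 and 2 at Visit 5. The lower bound is max(3, 2) = 3 and the upper bound is 3 + 2 = 5. In the boosted group that is 3/20 = 15% to 5/20 = 25%.

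*All variables, two visits.* 10 x 2 = 20 tables. Assume each shows k subjects out of range and N = 50:

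| k (assumed) | lower bound | upper bound, min(50, 20k) |
|---|---|---|
| 1 | 1 | 20 |
| 2 | 2 | 40 |
| 3 | 3 | 50 |
| 5 | 5 | 50 |

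The baseline rows of a shift table could narrow these ranges where subjects start in different categories. They help little here, because Protocol 3.1 asks for screening tests within normal values, so most subjects should start in the same row.

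**When can an unscheduled draw arise?** Taking the 21 days after vaccination as Days 2 to 22, the Visit 2 window covers 2 of them. 21 - 2 = 19, and 19/21 = 90%. This is a share of calendar days on which a symptom-triggered count would fall outside a scheduled visit. It is not a share of samples or subjects, since a draw happens only if the subject is symptomatic.

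**Which unscheduled draws can add a subject?** Weekly repeats follow a neutropenia already found. If it was found at a scheduled visit, the subject is already out of range there. The fever or infection draw is the one that can reveal a new abnormality between visits.

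**Do the other outputs fill the gap?**
- Flagged listings: yes, by counting distinct subjects with a flagged post-vaccination value. This gives the exact number, but it is a hand count and not a planned summary.
- By-subject listing: only for subjects with a clinically significant value.
- Adverse event tables: Protocol 7.1.7 sends clinically significant abnormalities to the adverse event form. The endpoint is the wider set of deviations from normal.
- Adverse events of special interest (AESI) table: among blood counts this covers neutropenia only. Protocol 7.1.4.1 ties the definition to 7 days after vaccination, while Protocol 5.4 speaks of any time during the study. Those sections need to be reconciled; until then a neutropenia first seen on Day 13 is not certain to reach this table.

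**The case against.** A reader might infer that by-visit tables are the only laboratory output, that the subject count cannot be derived, or that unscheduled results are never tabulated. The documents support none of these. The same SAP section plans listings that flag every out-of-range value, and for at most 50 subjects the count can be read from them exactly. The phrase about time-point of assessment does not exclude unscheduled draws. The table shells are standard ones that SAP Annex 3 does not reproduce, so silence is not proof of exclusion.

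A reader might also infer that the counts most likely to reveal neutropenia are lost to the tables. That too goes beyond the text. Protocol 7.1.5 puts AESIs of any grade on the adverse event page, and SAP 6.5.2.3 summarises them from Day 1 to termination. A neutropenia recorded that way is tabulated. The weakness in this route is the 7-day wording already noted.

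Two further objections have force. First, the endpoint does not literally say any abnormality across variables. Read per variable, the shift tables do report it visit by visit for scheduled samples. Even so, two post-vaccination visits need a rule for counting a subject once. Second, an any-time count rises with the number of samples, and febrile or neutropenic subjects are sampled more often. That stands as a cost of the fix.

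**Conclusion.** The point holds in a limited form. SAP 6.5.2.5 names no summary that counts each subject once for endpoint (a), and states no rule for unscheduled haematology. The values exposed are those first found out of range between Day 8 and Day 85 that are neither clinically significant nor recorded as an AESI; as written, these may appear only in the flagged listings.

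The number of subjects affected cannot be estimated, because the documents give no abnormality or fever rate. The 3-to-5 range and the values of k are illustrations. For scale, one uncounted subject among 20 boosted is 1/20 = 5 percentage points. This is a descriptive secondary endpoint in a Phase 1 trial of up to 50 subjects, so no conclusion of the trial turns on it. The change is still worth making: it reports the endpoint as defined, from data already collected.

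**What to change.** Keep the by-visit tables and add to SAP 6.5.2.5:

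1. By group, the number and percentage (n/N) of subjects with at least one value below or above the normal range at any assessment from vaccination to study termination, scheduled or unscheduled. Give this overall and per variable.
2. A shift table from screening to worst post-vaccination value, with lowest and highest shown separately.
3. A sentence on how values already out of range at screening are handled.
4. A footnote that any-time counts depend partly on how often a subject was sampled, and should be read beside the scheduled-visit tables.

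The cost is one or two extra tables from data already in the eCRF, with no change to any study procedure. Any-time counts may exceed the by-visit counts, and groups with more symptom-triggered draws will be less directly comparable on them; the scheduled-visit tables remain the like-for-like comparison.
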